1.2 BACKGROUND ON ALECTINIB

1.2.1 Background on Tumor-Agnostic Drug Development

In recent years, there has been a shift in cancer treatment practices based on improved understanding of oncogenic signaling processes, as opposed to an "all-comers" approach (Gambardella et al. 2020). Molecular alterations in specific kinases often result in constitutive activation of cell proliferation and survival pathways, which can drive the initiation and progression of malignancy. This is particularly evident in NSCLC, for which numerous targeted therapies have been approved and adopted in clinical practice for specific molecularly defined populations, such as patients with NSCLC harboring EGFR-activating mutations, ALK fusions, and ROS1 rearrangements (National Comprehensive Cancer Network [NCCN] 2020).

More recently, this biomarker-driven treatment paradigm has gone beyond the confines of histologically defined tumors to be applied more broadly, regardless of tumors site of origin, in the so-called tumor-agnostic setting. This approach considers treatment based on known oncogenic drivers/genomic alterations to be more relevant than histology for the purpose of defining treatment strategies.

The tumor-agnostic setting has been recently validated by the U.S. Food and Drug Administration's (FDA's) approvals of NTRK inhibitors, such as larotrectinib and entrectinib in metastatic solid tumors expressing the TRK fusion oncogene, regardless of tumor's primary origin and histology. The efficacy of larotrectinib was investigated in 55 adult and pediatric patients across 17 unique TRK fusion–positive tumor types (Drilon et al. 2018). The response rate across multiple tumor types was 75% (95% CI: 61% to 85%) by independent review and 80% (95% CI: 67% to 90%) by investigator assessment (Drilon et al. 2018). Entrectinib was investigated in 54 patients across

Alectinib—F. Hoffmann-La Roche Ltd 25/Protocol BO41929, Version 4

10 different tumor types and 19 different histologies (Doebele et al. 2020). The response rate across tumor types was 57% (95% CI: 43% to 71%), and median duration of response (DOR) was 10 months (95% CI: 7.1 months to not estimable).

In addition, pembrolizumab, a PD-1 inhibitor, has received FDA approval in the tumor-agnostic setting in microsatellite instability–high or mismatch repair–deficient metastatic solid tumors. The efficacy of pembrolizumab was investigated across five single-arm clinical trials in 149 patients with 15 different solid tumor types that were microsatellite instability high or mismatch repair deficient positive (Marcus et al. 2019). The overall objective response rate (ORR) was 39.6% (95% CI: 32% to 48%), with DOR ranging from 1.6 months to 22.7 months.

These approvals demonstrate that therapies aimed at well-characterized oncogenic markers can deliver significant benefit and represent promising personalized treatment option regardless of tumor's site of origin and histological type.

1.2.2 Alectinib

Alectinib (also referred to as RO5424802 or CH5424802) is an oral small molecule, highly selective and potent next-generation ALK inhibitor with benzo[b]carbazole scaffold. In enzyme inhibition assays performed in vitro, this compound has been shown to selectively inhibit ALK and RET. Alectinib also shows in vitro and in vivo anti-tumor activity against tumor cell lines harboring ALK translocations, ALK alterations, and neuroblastoma lines harboring ALK-activating mutations. Alectinib is not a substrate of efflux transporters (such as P-glycoprotein [P-gp]) in the blood–brain barrier and is therefore able to distribute into and be retained within the CNS leading to high levels of CNS drug exposure.

Alectinib was approved in the United States, Canada, the European Union, and several other countries at a dose of 600 mg twice a day (BID) for the treatment of patients with ALK-positive metastatic NSCLC who have progressed on or are intolerant to crizotinib. This indication was approved by the FDA on the basis of the ORR and DOR observed in two single-arm pivotal studies (NP28761 and NP28673), demonstrating a combined ORR of 51% in this crizotinib-failed population and median DOR of 14.9 months (Yang et al. 2017). Efficacy in the CNS was also assessed in these trials, with a combined CNS response rate of 64% observed in patients with measurable CNS disease at baseline (Gadgeel et al. 2016). The most common adverse events (occurring in >20% of patients) observed in the combined analysis were constipation (38%), fatigue (34%), peripheral edema (28%), myalgia (25%), nausea (23%), cough (21%) and headache (21%). Reported adverse events were mostly of Grade 1 or Grade 2 severity, and no Grade \geq 3 adverse event occurred with a frequency of more than 5%, the most common being increased blood CPK (4%), dyspnea (4%), increased ALT (3%), and increased AST (3%). Adverse events leading to dose modification or interruptions occurred in 33% of patients, whereas adverse events leading to treatment withdrawal were reported in 6% of patients (Yang et al. 2017).

Alectinib—F. Hoffmann-La Roche Ltd 26/Protocol BO41929, Version 4

Alectinib has also been approved in the first-line setting on the basis of the data observed in BO28984 (ALEX), a randomized, open-label Phase III study of alectinib versus crizotinib in treatment-naive patients with ALK-positive NSCLC. The study showed a clinically meaningful and statistically significant improvement in investigator-assessed PFS of alectinib compared with crizotinib. At the updated data cutoff (1 December 2017), the PFS stratified hazard ratio was 0.43 (95% CI: 0.32 to 0.58) and median PFS with alectinib was 34.8 months (95% CI: 17.7 months to not evaluable) versus 10.9 months (95% CI: 9.1 to 12.9 months) with crizotinib (Camidge et al. 2019). Alectinib has also shown considerable activity in the CNS, with CNS response rates of 81% in patients with measurable CNS disease at baseline (Peters et al. 2017), and a median PFS in patients with CNS metastases at baseline of 27.7 versus 7.4 months for crizotinib (hazard ratio=0.35; 95% CI: 0.22 to 0.56) (Camidge et al. 2019). The safety profile of alectinib was consistent with that previously observed in trials conducted in patients who had previously received treatment with crizotinib. At the primary analysis, despite the longer treatment duration in the alectinib arm compared with the crizotinib arm (17.9 months and 10.7 months, respectively), alectinib appeared to be better tolerated than crizotinib, as shown by the lower incidence of patients with adverse events that were Grade ≥ 3 in severity (41% vs. 50%), leading to treatment interruptions (19% vs. 25%) and dose reductions (16% vs. 21%) (Peters et al. 2017).

Refer to the Alectinib Investigator's Brochure for details on nonclinical and clinical studies.

1.3 BACKGROUND ON THE DECENTRALIZED STUDY MODEL

Clinical trials have made rapid advances in terms of digitalization and decentralization (Laegemiddelstyrelsen 2021). Digital tools have reduced the need for patients to attend appointments at a hospital or similar clinical setting. Such tools enable digital consent and electronic consultations, and can include electronic data collection systems, wearables, and other medical devices. These advances make it possible to conduct decentralized clinical trials that promote health service equality, allowing patients to participate in clinical trials, regardless of their mobility or proximity to hospitals. This ensures a wider representation of trial participants, which is likely to facilitate the recruitment and retention of patients in clinical trials.

The benefit of a decentralized study model is that patients can be treated at home. This eliminates the need for them to travel long distances for clinic visits and provides an opportunity for patients with rare diseases to participate in a clinical trial. In this model, the investigator can treat and monitor the patient remotely (via telemedicine) in the physical presence of a mobile health care professional (mHCP). Protocol assessments can be conducted at the patient's home by the mHCP with the investigator present via telemedicine. In this model, the mHCP can collect and prepare all samples for shipment to the analytical lab, with imaging investigations being conducted at a facility identified and set up for the study close to the patient's home. The investigator can make referrals

Alectinib—F. Hoffmann-La Roche Ltd 27/Protocol BO41929, Version 4

to a specialist if additional investigations are needed to ensure patient safety, as in the traditional clinical trial model. The logistics of conducting a decentralized study may differ according to local requirements and investigator preference.

In the context of the current study, ALK positivity may be determined using local or centralized testing results, making it is impossible to predict where identified patients will be located. Therefore, given the targeted population, the rarity of ALK positivity, and the approach used to identify patients, a decentralized approach has been chosen for this study.

1.4 STUDY RATIONALE AND BENEFIT–RISK ASSESSMENT

This trial will assess the efficacy and safety of alectinib in ALK-positive solid tumors other than lung cancer. For the purposes of this study, ALK positivity is defined as ALK fusions or the selected ALK-activating mutations R1275Q, F1245C, F1174X (with X being any other amino acid). Patients enrolled in this study will represent a population with a high-unmet medical need because patients will be eligible only if they have either exhausted or are unsuitable to receive the standard-of-care treatment for their diagnosed malignancy.

Alterations in ALK have been shown to be an important mechanism of oncogene addiction in many tumor types (Hallberg and Palmer 2013; Ross et al. 2017), and although these alterations are rare in non-NSCLC tumors, evidence of clinical benefit from ALK inhibitors in a variety of ALK-driven malignancies exists. Efficacy of ALK inhibitors have been reported in nonclinical models of neuroblastoma harboring ALK-activating mutations, such as F1174L, F1245C, and R1275Q (Trigg and Turner 2018). In addition, clinical benefit has been described with alectinib in a patient with small cell carcinoma of the prostate harboring the F1174C ALK mutation (Carneiro et al. 2018).

Clinical benefit has also been reported with ALK inhibitors in patients with various solid tumors harboring ALK fusions, such as cancer of unknown primary (CUP) site, IMT, colorectal cancer, and thyroid cancer (Amatu et al. 2015; Godbert et al. 2015; Yakirevich et al. 2016; Gambacorti-Passerini et al. 2018), and with alectinib in papillary renal cell carcinoma (Pal et al. 2018), metastatic IMT (Saiki et al. 2017; Honda et al. 2019) and large cell neuroendocrine carcinoma (Shimizu et al. 2019). Of note, while most of the efficacy data for alectinib, particularly in the clinical setting, are based on inhibition of the EML4-ALK fusion protein (the most abundant fusion protein observed in NSCLC), evidence of alectinib activity in other types of ALK fusion proteins exist. In the ALEX trial of alectinib versus crizotinib in treatment-naive patients with ALK-positive NSCLC, 11 patients enrolled in the alectinib arm were identified to harbor fusion partners other than EML4 (KLC1, BCL11A, FTO, KIF5B, BRE, MAP4K3 LM07, and ORC5). Of these, 10 patients achieved a best overall response of a partial response (PR), and one experienced stable disease (Roche data on file).

In patients with ALK-positive NSCLC, alectinib has proven to be a potent, well tolerated, brain-penetrant ALK inhibitor at the approved dosage of 600 mg BID, and there is no reasonable expectation that the safety profile observed with alectinib in patients with ALK-positive NSCLC should differ significantly when administered to patients with other solid tumors. Therefore, it is expected that alectinib in the population enrolled in this study will show a favorable benefit–risk profile.

Identified and potential risks associated with alectinib treatment will be closely monitored throughout the clinical program. Patients' safety during the study is optimized by targeting the most appropriate patient population through inclusion and exclusion criteria, stringent safety monitoring by the Sponsor, and protocol-specified study drug modification criteria (see Section 5.1.2).

The role of ALK alterations in different tumor types, combined with the promising clinical activity described above in non-NSCLC tumors, supports further investigation of alectinib in the tumor-agnostic setting for patients with solid tumors harboring ALK fusions or selected ALK-activating mutations (such as the one described in neuroblastoma), for whom no alternative standard therapy is suitable.

1.4.1 Trial-Specific Risk Assessment

Alectinib is an approved drug in NSCLC. In this setting, it is prescribed by oncologists and taken by patients at home BID. If this was a traditional study rather than a decentralized study, patients would be asked to take alectinib at home as per investigator instructions. Moreover, the safety assessments to be completed at the patient's home in this study are the same as those that would be completed at an in-clinic visit. More frequent safety visits are scheduled during the first 3 months in order to closely monitor initial patient exposure to alectinib. In addition, patients will be instructed to take the first dose in the presence of an mHCP.

This study allows both virtual and physical study sites (see Appendix 9 and Section 3.3.1).

The following elements are associated with the decentralized nature of the study:

- Telemedicine
 - The investigator and clinical research coordinator (CRC) will be in remote contact with the patient.
 - An mHCP will perform protocol-mandated assessments and will collect and prepare all samples for shipment to an analytical laboratory.
 - *A smartphone* will be provided to the patients with an application that facilitates connection with the investigator and CRC.
- Electronic ICF
- At-home investigational medicinal product (IMP) delivery
- Local imaging center close to the patient's home

Alectinib—F. Hoffmann-La Roche Ltd

29/Protocol BO41929, Version 4

Overall, based on the expected favorable benefit–risk profile of alectinib in this study, the decentralization elements stated above, the patient population to be enrolled, the well-characterized and tolerated safety profile of alectinib and its route of administration along with the standard practice, the risks associated with decentralization are expected to be similar to those in a *traditional* study.

In this decentralized study, all included elements have been designed to enable operating as close as possible to the level of a non-decentralized study.

- Investigator and Sponsor have exactly the same responsibilities, as outlined in the International Council for Harmonisation of Technical Requirements for Registration of Pharmaceuticals for Human Use (ICH; E6R2).
- Safety management performed remotely will follow the same approach as management for a non-decentralized trial.
 - There will be more frequent safety visits during the first 3 months in order to closely monitor initial patient exposure to alectinib.
 - Patients will be instructed to take the first dose in the presence of an mHCP.
 - The investigator will make arrangements for referrals to a specialist if additional investigations to the study protocol are needed to ensure patient safety.
- All drug shipments will be temperature controlled and bottles pre-labelled for clinical trial use. The mHCP will check bottle integrity and label and provide instruction to patient on how to take the medicine.
- The mHCP will be a trained, experienced, and qualified healthcare professional. Assessments and supervision of the mobile healthcare professional will be performed in the remote presence of the investigator.

1.4.2 COVID-19 Benefit–Risk Assessment

In the setting of the coronavirus disease 2019 (COVID-19) pandemic, patients with comorbidities, including those with cancer, are a more vulnerable population, with the potential for more severe clinical outcomes from COVID-19. However, it is unclear whether or how cancer therapies such as chemotherapy and targeted therapy impact the incidence or severity of COVID-19. Based on its safety profile and mechanism of action, it is not anticipated that the treatment used in this study will increase the risk of infection with severe acute respiratory syndrome coronavirus 2 (SARS-CoV-2). Clinical trials with the treatment in this study have been ongoing during this pandemic and, although the study numbers are small, enrolled patients have not shown any increased risk of developing COVID-19 symptoms.

Study BO41929 is home based, utilizing mHCPs, who would continue to observe the *applicable epidemiologic/public health and hygiene measures*, and telemedicine visits with the investigator.

1.4.2.1 COVID-19 Vaccines

Based on a specific benefit–risk assessment, taking into account the available relevant information, the approved non-live COVID-19 vaccines may and should be administered in patients who are in the study, as long as there is no other contraindication (e.g., known hypersensitivity to a vaccine component).

Although there is no specific requirement regarding the timing of vaccine administration, the vaccination should ideally be at least commenced before study enrollment and initiation of study drug, whenever possible.

Details of any COVID-19 vaccination received before study enrollment should be captured in the medical history section, at screening, whereas details regarding the COVID-19 vaccine received during the study should be recorded in the concomitant medication section.

Investigators should share with patients' primary healthcare providers relevant information regarding any potential effect of respective study drugs on the response to COVID-19 vaccination, as applicable. Also, patients should contact the investigators or site staff, when they are invited to receive a COVID-19 vaccine deployed in their region. The decision to vaccinate a patient should be based on a patient's SARS-CoV-2 infection/complication risk, general health condition, severity of underlying malignancy, and regional epidemiology of COVID-19. COVID-19 vaccines should be administered in accordance with their respective prescribing information and applicable immunization guidelines.

After COVID-19 vaccination, one should continue to observe the applicable epidemiologic/public health and hygiene measures during the pandemic, along with per protocol safety measures and assessments in order to minimize the risk and to appropriately identify and assess potential adverse reactions (e.g., nausea, diarrhea, myalgia) possibly shared by vaccines and study drugs.

Based on the published mechanism of action of the COVID-19 vaccines and the known mechanism of action of alectinib, there is no scientific rationale to expect that COVID-19 vaccines will affect the efficacy of alectinib.

2. OBJECTIVES AND ENDPOINTS

This study will evaluate the efficacy and safety of alectinib in patients with ALK-positive locally advanced or metastatic solid tumors other than lung cancer. Specific objectives and corresponding endpoints for the study are outlined below.

2.1 EFFICACY OBJECTIVES

2.1.1 Primary Efficacy Objective

The primary efficacy objective is to demonstrate a clinically relevant response to experimental treatment on the basis of the following endpoint:

 Confirmed ORR, defined as the proportion of patients with a complete response [CR] or a PR ≥28 days after initial response in patients with solid tumors, as determined by the investigator according to Response Evaluation Criteria in Solid Tumors, Version 1.1 (RECIST v1.1)

The primary efficacy objective of the trial is to evaluate alectinib at the dose of 600 mg BID until disease progression, death, or withdrawal for any other reasons in patients with ALK fusion solid tumors (excluding enrolled patients with CUP and CNS primary tumors) with measurable disease at baseline who have a baseline tumor assessment per the investigator according to RECIST v1.1 and receive at least one dose of alectinib (response-evaluable population).

The primary evaluation will be made regardless of whether patients withdraw from treatment, withdraw consent, or receive additional or alternative therapy.

2.1.2 Secondary Efficacy Objective

The secondary efficacy objective for this study is to evaluate the efficacy of alectinib in patients with ALK-positive solid tumors in the response-evaluable population, defined according to the investigator or by blinded independent center review (BICR), depending on who is assessing the endpoint, on the basis of the following endpoints:

- Confirmed ORR, defined as the proportion of patients with a CR or PR ≥28 days after initial response by BICR according to RECIST v1.1
- Duration of response (DOR), defined as the time from the first occurrence of a documented objective response to disease progression or death from any cause (whichever occurs first), as determined by both the investigator and by BICR according to RECIST v1.1
- Progression-free survival (PFS), defined as the time from first dose of alectinib treatment to disease progression or death from any cause, as determined by both the investigator and BICR according to RECIST v1
- CNS ORR, defined as objective tumor response rate (a CR or a PR) of CNS lesions in patients with measurable CNS metastases at baseline by BICR according to RECIST v1.1
- CNS DOR, defined as the time from the first observation of CNS response until the first observation of CNS progression or death from any cause by BICR according to RECIST v1.1
- Overall survival (OS), defined as the time from first dose of study drug to death from any cause

For patients with primary CNS tumors with measurable disease at baseline who have a baseline tumor assessment per the investigator according to Response Assessment in Neuro-Oncology (RANO) criteria and receive at least one dose of alectinib:

- ORR, DOR, and PFS in all ALK fusion–positive patients who have measurable disease at baseline as determined by both the investigator and BICR
- OS

For patients with solid tumors without ALK fusions, harboring defined ALK mutations (R1275Q, F1245C, F1174X, with X being any other amino acid) and receive at least one dose of alectinib:

- ORR, DOR, and PFS as determined by the investigator and by BICR according to RECIST v1.1
- CNS ORR and DOR in patients with CNS metastases at baseline by BICR according to RECIST v1.1
- OS

For patients with CUP who receive at least one dose of alectinib:

- ORR, DOR, and PFS as determined by both the investigator and BICR according to RECIST v1.1
- CNS ORR and DOR in patients with CNS metastases at baseline, as determined by BICR according to RECIST v1.1
- OS

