Response will be assessed by the investigator on the basis of the CT and MRI scans according to RECIST v1.1 (see Appendix 5) or, for patients with primary CNS tumors, RANO criteria, which include neurological examination and corticosteroid use (see Appendix 6).

In addition, scans will be sent for BICR for assessment of responses according to RECIST v1.1 and, for patients with primary CNS tumors, according to RANO criteria.

Assessments performed by BICR will not be shared with the investigator and will have no impact on the management of the patient.

Tumor assessments performed as standard-of-care prior to obtaining informed consent and within 28 days prior to the first dose may be considered as baseline assessment if they satisfy the protocol criteria.

Scheduled tumor assessments should be kept according to the original scheduled based on the date of first dose administration, regardless of clinical visits delays and drug interruptions. At the investigator's discretion, tumor assessment may be repeated at any time if progressive disease is suspected (for example, in case of symptomatic deterioration).

An objective response should be confirmed by repeat assessments at least 4 weeks after initial documentation. No additional assessment is planned for 4 weeks after the initial response, but every effort should be made to obtain confirmation of response, even if a patient who has initially responded is withdrawn from study treatment for any reasons other than progression or death.

Patients who discontinue study treatment for any reason other than progression of disease or death should continue to have regular disease assessments every 8 weeks per the schedule of assessments (see Appendix 1) until progression.

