If alectinib is prematurely discontinued for reasons other than disease progression, off-treatment disease assessments must continue until radiological progression of the disease as per schedule of activities (see Appendix 1). Following progression, patient status, and subsequent therapies will be captured as long-term follow-up every 3 months until death, patient withdrawal of consent, or termination of the study, whichever occurs first.

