6.4 EFFICACY ANALYSES

6.4.1 Primary Efficacy Endpoint

The primary efficacy endpoint is ORR as assessed by investigator per RECIST v1.1, defined as the proportion of patients with an objective response. An objective response is defined as a CR or a PR per RECIST v1.1. Confirmation of objective response is required (confirmed \geq 28 days apart in two separate tumor assessments). Patients not meeting this criterion (including patients without a post-baseline tumor assessment) will be considered as non-responders.

An estimate of the ORR and its 95% CI using the Clopper-Pearson method will be calculated.

The primary efficacy analysis population consists of all patients with ALK fusion–positive solid tumors (excluding patients with CUP and primary CNS tumors) with measurable disease at baseline who have a baseline tumor assessment per the investigator according to RECIST v1.1 and have received at least one dose of study treatment.

An interim analysis will be performed as described in Section 6.9.

The primary analysis will take place once all patients have been followed for a minimum of 24 weeks (i.e., three tumor assessments) to allow confirmation of any observed CR or PR, unless they progressed or withdrew from sooner from the study.

6.4.2 Secondary Efficacy Endpoints

The secondary efficacy endpoints are presented in Section 2.1.2.

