#### Table 1 Objectives and Corresponding Endpoints (cont.)

#### 1.1.1 Expression of Objectives and Endpoints using the Estimand Framework

The primary study objective and corresponding endpoint, as well as the main secondary efficacy objective and the corresponding secondary efficacy endpoints, are expressed using the estimand framework in Table 2, in accordance with the International Conference on Harmonization E9 (R1) statistical principles for clinical trials (ICH 2020).

Primary Efficacy Objective			Estimand Definition
•	To demonstrate a clinically relevant response to alectinib treatment	• Pc (e: tui ba to (re	opulation : Patients with ALK fusion solid tumors xcluding enrolled patients with CUP and CNS primary mors) with measurable disease at baseline who have a seline tumor assessment per the investigator according RECIST v1.1 and receive at least one dose of alectinib esponse-evaluable population)
		• Va pa in inv	ariable : Confirmed ORR, defined as the proportion of tients with a CR or a PR $\ge$ 28 days after initial response patients with solid tumors, as determined by the vestigator according to RECIST v1.1
		• Tr Bl otl	eatment : Experimental: alectinib at the dose of 600 mg D until disease progression, death, or withdrawal for any her reasons
		• Int	ercurrent events:
		• St	art of additional or alternative therapy
		• Ea	arly discontinuation from study treatment r any reason or withdrawal from study
		• Ha reg ap	andling of intercurrent events: A treatment policy with gards to the intercurrent events listed above will be oplied for the primary analysis.
		• Sι	ummary measure : Confirmed ORR
Main Secondary Efficacy Objective			Estimand Definition
•	To demonstrate a clinically relevant response to alectinib treatment	● Ac	cording to the blinded independent center review (BICR)

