## 5.3 PRIMARY ENDPOINT ANALYSIS

## 5.3.1 Definition of Primary Endpoint

The primary efficacy endpoint is confirmed ORR as determined by the investigator in patients with ALK fusion solid tumors (excluding enrolled patients with CUP and CNS primary tumors). An objective response is defined as a CR or a PR according to RECIST v1.1. Confirmation of objective response is required (confirmed ≥ 28 days apart in two separate tumor assessments). Patients not meeting this criterion (including patients without a post-baseline tumor assessment) will be considered as non-responders. ORR is defined as the proportion of patients with measurable disease at baseline who have an objective response in the response-evaluable population.

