# 5.3.2 Main Analytical Approach for Primary Endpoint

An estimate of the confirmed ORR and its two-sided 95% CI using the Clopper-Pearson method will be calculated. The confirmed ORR will be tested against the minimal clinically relevant ORR of 30% in this tissue-agnostic, biomarker-defined population with no available treatment options at the 5% two-sided significance level, i.e., the lower limit of the Clopper-Pearson CI must be bigger than 30%.

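### A response first seen after a pre-progression switch to another anti-cancer drug counts in the primary ORR, and no planned analysis shows the result without it (minor, cheap to fix)

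*Protocol*

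**What the plan says.** **Estimand.** Protocol 2.1.1: "The primary evaluation will be made regardless of whether patients withdraw from treatment, withdraw consent, or receive additional or alternative therapy". SAP Table 2 names the start of additional or alternative therapy as an intercurrent event and applies treatment policy to it. The two documents agree.

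**Responder rule.** SAP 5.3.1: "An objective response is defined as a CR or a PR according to RECIST v1.1", with confirmation at least 28 days apart. Nothing in that section stops the count when another anti-cancer therapy begins.

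**Scanning after alectinib.** Under Protocol 4.7.1, using an anti-cancer therapy outside the protocol ends study treatment but not imaging. Protocol 4.6.5 says that patients who stop for reasons other than progression or death "should continue to have regular disease assessments every 8 weeks per the schedule of assessments". Protocol 4.7.1 says that "off-treatment disease assessments must continue until radiological progression of the disease as per schedule of activities".

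**Success criterion.** SAP 5.3.2 tests against a fixed 30%: "the lower limit of the Clopper-Pearson CI must be bigger than 30" per cent.

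**Planned checks.** SAP 5.3.3 only points to 5.1, where the BICR analysis serves as the sensitivity analysis. SAP 5.4.1 analyses the BICR endpoint in the same way as the primary. SAP 5.3.4 contains subgroups only. SAP 5.7.2 summarizes subsequent anti-cancer therapy but does not relate its start to the date of response.

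**The concern.** The primary objective in SAP Table 1 concerns response to alectinib. With no control arm, treatment policy has no comparator in which later therapy could balance out. A response produced by a second drug is simply added to the numerator, so any effect on the ORR is upward.

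The BICR read changes who measures the tumour, not which responses are eligible, so it cannot reveal this. If the result falls near the threshold and even one such response is in it, the planned outputs would not show whether the conclusion depends on that patient.

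**Working it through.** **1. Is the route open within the planned follow-up?** Minimum follow-up is 24 weeks with scans every 8 weeks (Protocol 6.4.1 and 4.6.5), that is, at about weeks 8, 16 and 24. A patient who switches before week 16 can have a first response at week 16 and confirmation at week 24. The gap is 56 days, which meets the 28-day rule.

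**2. The plan's own figure.** The Clopper-Pearson lower limit for r of 50 is the 2.5th percentile of Beta(r, 51 − r).
- r = 23: 31.81%, matching SAP Table 3.
- r = 22: 29.99%, which fails.

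Success therefore means at least 23 responders. SAP section 3 uses 46% (23/50) as its planning value, which is exactly the smallest passing result.

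**3. Chance of success with no switchers,** P(X ≥ 23) for X ~ Bin(50, p):
- p = 0.30: 0.0123
- p = 0.40: 0.2340
- p = 0.46: 0.5548 (the plan's stated 70% power is close to a normal approximation, 0.680 to 0.695, and is a separate matter)

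**4. Assumptions.** The documents do not say how many non-responders switch before progression (m) or what share of them then respond (q). I take m = 1 to 3 and q = 20 to 40%. Three of 50 is an upper-end illustration: Protocol 1.2.2 reports 6% adverse-event withdrawal in NSCLC, and 0.06 × 50 = 3. Many such patients would already have responded, or would start nothing new before progression.

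**5. Expected ORR inflation** = m × q / 50. The low end is 1 × 0.2 / 50 = 0.4 percentage points; the high end is 3 × 0.4 / 50 = 2.4 points.

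**6. Chance of success at a true ORR of 30%.** Model A uses an effective rate p + (m/50)q. Model B lets m non-responders switch, each responding with probability q.

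| m | Model A, q = 0.2 / 0.4 | Model B, q = 0.2 / 0.4 |
|---|---|---|
| 1 | 1.45% / 1.70% | 1.48% / 1.74% |
| 2 | 1.70% / 2.31% | 1.78% / 2.41% |
| 3 | 1.99% / 3.09% | 2.12% / 3.27% |

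Check of Model B, m = 1, q = 0.4: 0.01228 + P(X = 22) × 0.4 = 0.01228 + 0.01281 × 0.4 = 0.0174.

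**7. Gain in the chance of success from one switcher** = P(X = 22) × q, for q = 0.2 to 0.4:
- p = 0.30: 0.01281 × q = 0.3 to 0.5 points
- p = 0.40: 0.09588 × q = 1.9 to 3.8 points
- p = 0.46: 0.10861 × q = 2.2 to 4.3 points

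**The case against.** **It is a declared choice, stated the same way in both documents.** This stands. A reader might infer an error or a contradiction between Protocol and SAP; there is none. What is missing is an analysis showing how much the choice matters.

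**The effect is small.** This largely stands. A reader might infer that the type I error is broken. The figures do not support that: the exact test starts at 1.2%, and with one or two switchers it stays below the nominal 2.5% upper tail at either assumed response rate. The assumed rates may also be generous, because the SAP describes patients with no other treatment available. The counted event is demanding too: no progression yet, a 30% fall from the original baseline (Appendix 5), scans continued although patients may stop them (Protocol 4.7.2), and confirmation. With q = 10%, also an assumption, three switchers give about 1.6%. Any single reclassified patient can decide a 50-patient exact test.

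**Responses on later lines after progression.** A reader might infer that these count as well. The follow-up does not support it: "Following progression, patient status, and subsequent therapies will be captured as long-term follow-up every 3 months", with no off-treatment scans planned at that stage.

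**The data are already captured.** This stands in part. A reader might infer that switch dates go unrecorded. In fact, the reason for stopping alectinib goes on the eCRF (Protocol 4.7.1), and concomitant medication is recorded to 28 days after the last dose (Protocol 4.5). The adverse-event window in Protocol 6.5 also presupposes a start date within that period. Appendix 1 footnote c collects further cancer therapies every 3 months and is not limited to the time after progression. What remains unclear is a switch more than 28 days after the last dose and before progression. The off-treatment column lists only scans, and footnote c does not say when its collection starts. Whether the eCRF covers this cannot be judged from these documents.

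**Conclusion.** The point holds as a minor, inexpensive improvement. The route follows from three rules read together (treatment policy, scanning to progression, no new-therapy cut-off) rather than from any single sentence. The direction of the bias is certain; its frequency is unknown and probably low.

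Under the assumed 1 to 3 switchers and 20 to 40% response, the chance of success at a true ORR of 30% moves from 1.2% to between 1.4% and 3.3%, and exceeds 2.5% only in the most extreme combination. The practical stake is a result near 22 or 23 of 50, where the planned outputs could not show whether the conclusion rests on another drug's response.

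**What to change.** Keep treatment policy as the primary analysis.

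1. **SAP 5.3.4:** pre-specify one supplementary analysis of confirmed ORR, for investigator and BICR, in which a CR or PR first documented after the start of an anti-cancer therapy outside the protocol (the trigger already used in Protocol 4.7.1) counts as non-response. A response first seen before the switch and confirmed after it remains a response. It belongs in 5.3.4 rather than 5.3.3 because changing the intercurrent-event strategy asks a different question from the primary estimand.
2. **Output:** report the number of such responses, with a listing of first-response date against new-therapy start date. If there are none, the listing is empty and the question is closed.
3. **Data capture:** clarify that the start date of new anti-cancer therapy is also recorded when it begins more than 28 days after the last alectinib dose and before progression.

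The cost is one derivation, one listing and a short clarification. The downside is that the supplementary ORR may be slightly lower. Because scans are 8 weeks apart, it may also exclude a genuine alectinib response first imaged just after a switch.
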